2. THE ENDOMETRIUM

The female upper genital tract is a site of mucosal-associated lymphoid tissue (MALT). While their functions obviously differ, endometrium shares several characteristics with GALT. (*See Appendix A: Comparison of Endometrium to GALT.*) Endometrium is distinguished by the presence of a unique immune cell component — uterine natural killer (NK) cells, the ability to receive and tolerate an embryo and monthly cycles of proliferation, differentiation and tissue breakdown in response to endocrine and paracrine factors. Leukocytes comprise a substantial portion of endometrial cell constituents, ranging from 7% to 30% depending on ovulatory cycle phase. Polymorphonuclear leukocytes are common during menses, but T cells and macrophages, combined with the uterine NK cells, comprise 90% of endometrial leukocytes. T cells comprise approximately 50% of leukocytes; of these one half to two thirds are CD8+, and a smaller but cycle-constant proportion express CD4. In contrast, the number and proportion of NK cells increases as the ovulatory cycle progresses. CD8 + T cells occur as stromal cells, intraepithelial lymphocytes and in lymphoid aggregates. Lymphoid aggregates or follicles are present in the basal layer, formed during the proliferative phase, and include a core of B-cells surrounded by CD8+CD45RO+CD45RA-, T cells with an outer halo of macrophages. Aggregates arise primarily from trafficking of cells to nucleation sites; a small number of CD8+ cells show evidence of division at the site. Macrophages account

for 5% to 15% of stromal cells. Phenotypically unique uterine NK cells are present in deep tissue layers.

Only eight reports have been published on the endometrium and HIV infection. Active HIV replication occurs in monocytes and macrophages in endometrium. Very limited information is available on the effects of HIV infection on endometrial tissue. Johnstone reported increases in CD45+ cells and CD3+ expression among HIV-positive women at the time of menses, compared with HIV-negative women. In a study of three HIV-infected women, White, *et al.*, found that despite the presence of HIV-specific cytotoxic T lymphocytes (CTL) in peripheral blood mononuclear cells (PBMCs), CTL activity was absent in the endometrium of the two antiretroviral therapy (ART) recipients, both of whom lacked endometrial CD8+ cells. By contrast, the one long-term nonprogressor (LTNP) studied demonstrated CD8+ cells and HIV-specific CTL in endometrium.

Clearly, this study can make significant contributions to the understanding of how the endometrial MALT site is affected by HIV, as well as investigating the potential value of endometrial tissue for future studies of MALT and HIV.

C. STUDY DESIGN AND METHODS

1. STUDY POPULATION AND SAMPLE SIZE

A total of 50 WIHS participants, 10 to 15 participants each from five phenotype groups, will be enrolled. Once 15 women from any of the categories have completed the study, that category will be closed to enrollment. The phenotype groups are as follows: (*See Appendix B for complete definitions.*)

- HIV-uninfected women
- Natural controllers
- Good CD4 responders to highly active antiretroviral therapy (HAART)
- Poor CD4 responders to HAART
- Off-treatment progressors

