
WOMEN'S INTERAGENCY HIV STUDY
 
SECTION 36: MALT/GALT SUBSTUDY PROTOCOL

A. STUDY PURPOSE

The purpose of this study is to evaluate the effects of HIV infection in gut-associated lymphoid tissue (GALT) and endometrial mucosal-associated lymphoid tissue (MALT) in HIV-negative and HIV-positive women at selected stages of HIV disease progression.

Our aims are to compare endometrial, ileal and sigmoid colon tissue samples in selected WIHS participants in order to determine if:

1. The perturbations in GALT, HIV-specific immune responses, apoptosis, and collagen deposition that have been reported in HIV-positive men are also found in HIV-positive women.
2. The patterns of these alterations differ among HIV disease state groups.
3. These alterations are similarly present in endometrial tissue.
4. HIV infection will be associated with reduced numbers of CD4 memory cells, increased lymphocyte activation, apoptosis, cellular turnover, T regulatory cells and collagen deposition in both gut and endometrium; the extent of the abnormalities will be directly correlated with intracellular levels of HIV RNA.
5. The extent of immune abnormality in MALT tissues will be correlated with the extent of HIV disease progression, and with expression of cellular activation markers and level of circulating soluble biologic mediators (in a pattern consistent with inflammation).
6. It is feasible to use endometrial tissue to evaluate overall mucosal lymphoid immunity in future HIV research.

B. BACKGROUND, SIGNIFICANCE, AND PRELIMINARY STUDIES

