2. STUDY PROCEDURES

a. Pre-eligibility:

WIHS sites will be provided with lists of potentially eligible participants based on the Inclusion and Exclusion Criteria listed below. Study staff will then approach potentially eligible participants at their next regularly scheduled Core Visit. Participants who are interested will have a Pre-Eligibility Screening Interview at the end of the Core Visit. Those who appear eligible will be scheduled for a Screening Visit. (*See Appendix C: Time and Events Schedule.*)

b. Screening Visit

The Screening Visit will be scheduled as soon as possible after the WIHS Core Visit. Informed consent will be obtained at this visit. All participants will answer questions about medical history, current medications, and use of intravaginal products. Urine testing for pregnancy will be performed. Participants with a positive pregnancy test will not continue in the study. Blood will be drawn for prothrombin and partial

thromboplastin tests (PT and PTT). HIV-positive participants will have blood drawn for HIV viral load, since it is anticipated that results from the prior WIHS Core Visit will not yet be available. HIV-positive participants will also be asked to report any acute medical illnesses occurring during the study period and to avoid vaccinations during the study if this can be done without compromising their health. These measures are requested because of the potential for HIV viral load changes associated with acute medical illness and vaccination.

Participants will be instructed how to perform at-home urine testing to detect luteinizing hormone (LH). LH peaks just before ovulation, and is detectable in the urine in the early luteal phase.

Study staff will dispense Clearblue brand LH surge kits (Proctor & Gamble, Cincinnati, OH) and assist the participant in determining when to start testing. (*See Appendix D: When to Start LH Surge Testing.*) The participant will notify site staff when LH is detected in the urine, so that the Endometrial Biopsy Visit can be scheduled within 7 to 9 days, at which time the participant will be in the mid-to-late luteal phase. Participants will be encouraged to contact site staff should *any* questions or concerns arise during urine testing. Study staff may also contact participants.

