- If the colonoscopist determines that the Bowel Prep is inadequate to allow visualization of the colon, s/he will withdraw the endoscope; the participant will remain in the unit to recover, but no further study procedures (i.e., endometrial biopsy) will be done. Blood, if drawn for serum progesterone level or HIV viral load, will be discarded.
- After colonoscopy is completed, all gynecological specimens will be collected. The participant will be placed in the lithotomy position. A pelvic examination will be performed to rule out signs of infection; if any are present, no further procedures will be performed.

1. Endocervical wick/sponge sampling:

Endocervical mucus and secretions for analysis of cytokines will be collected with Merocel ophthalmic sponges (Medtronic Xomed, Jacksonville, FL). Using a ring forceps, two sponges will be inserted sequentially into the cervical os; each will be held in place to absorb sample for 60 to 90 seconds. The sponges are inserted gently directly into the os. The depth of insertion is based on the size of the os; in some women it is possible to insert just the tip of the sponge, while in others, the entire sponge may be inserted. The sponges should never be forced, as this may cause bleeding which will contaminate the mucus collected. They should not be twisted or turned; simply allow the sponge to rest and absorb secretions. It should be possible to see the sponge expanding as it absorbs secretions.

After removal, the sponges will be placed in separate cryovials, supplied by the San Francisco site. Place the sponge spearhead down in the vial and cut off the part of the handle that protrudes from the vial so that the sponge will fit into the

tube. Then place this cut-off handle in the vial with the sponge section and close the vial. This is necessary because the lab must weigh the whole collection device in order to ascertain the volume of fluid collected. The cryovials will be placed in liquid nitrogen and the samples will be shipped frozen.

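### Section C.1: a total of 50, 10 to 15 per group and closure at 15 completers hold together only at exactly 10 per group, so the closing rule has no room to operate

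*Protocol*

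**What the plan says.** Two sentences in Section C.1 (Study Population and Sample Size) fix the numbers. The first gives the total and the group range: "A total of 50 WIHS participants, 10 to 15 participants each from five phenotype groups, will be enrolled". The second gives the only closing rule: "Once 15 women from any of the categories have completed the study, that category will be closed to enrollment". The groups are uninfected women, natural controllers, good and poor CD4 responders to HAART, and off-treatment progressors.

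On recruitment, Section C.2 says that sites receive lists of potentially eligible women, and "Study staff will then approach potentially eligible participants at their next regularly scheduled Core Visit". It does not say how places are shared among phenotypes. The protocol does not say whether enrollment stops at 50, or what happens if 50 is reached while a group is short.

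On losses before completion, Section C.2 ends participation for a positive pregnancy test, recent intravaginal product use, or disqualifying coagulation or viral load results. Signs of infection at the pelvic examination stop further procedures. After an inadequate bowel prep, "no further study procedures (i.e., endometrial biopsy) will be done". Section D allows re-enrollment after a failed bowel prep, at the site's discretion.

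Aim 2 in Section A asks whether "The patterns of these alterations differ among HIV disease state groups".

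**The concern.** The total equals the lower end of the group range multiplied by five, so the range has no slack. The eleventh woman in any group takes a place that another group needs to reach 10. The only stopping instruction acts at 15 completers, five places later.

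The two figures also use different units. The total counts women enrolled and the cap counts women who complete. A group may therefore enroll more than 15 before it closes, and 50 enrolled may yield fewer than 50 completers.

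The aims that compare disease-state groups are at stake. They depend on the size of the smaller groups, and the text does not protect the floor of 10. Group targets and category closure are instructions that sites follow during enrollment, so this is not a detail to leave to an analysis plan.

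**Working it through.** **Inputs, all from Section C.1:** total 50 (enrolled); 5 groups; range 10 to 15 per group; closure at 15 completers.

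**Step 1. The stated total.** Lower end: 5 × 10 = 50, which reproduces the stated figure. Upper end: 5 × 15 = 75, which does not. The range corresponds to 50 to 75 women.

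**Step 2. Splits that satisfy everything.** There are 20,176 ways to divide 50 over five labelled groups with none above 15. Exactly one keeps every group at 10 or more: 10/10/10/10/10.

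**Step 3. What follows if groups run to 15 within 50.**

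| Groups at 15 | Places left | Needed for 10 in each other group | Mean of the other groups |
|---|---|---|---|
| 1 | 50 − 15 = 35 | 4 × 10 = 40 | 35/4 = 8.75 |
| 2 | 50 − 30 = 20 | 3 × 10 = 30 | 20/3 = 6.7 |
| 3 | 50 − 45 = 5 | 2 × 10 = 20 | 5/2 = 2.5 |

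Keeping the floor with k groups at 15 needs 15k + 10(5 − k) women: 55, 60, 65, 70 and 75 for k = 1 to 5.

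**Step 4. Effect on pairwise contrasts (illustration).** The protocol states no test, alpha or power. I assume a two-sample t test, two-sided 5%, 80% power. The detectable difference d, in SD units, solves P(T > t(0.975, df)) = 0.80, where T is noncentral t with df = n1 + n2 − 2 and noncentrality d/√(1/n1 + 1/n2). The opposite tail is negligible. For 10 v 10: df = 18, critical value 2.101, √(1/10 + 1/10) = 0.447, d = 1.32.

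| Contrast | Detectable difference (SD) | Power at 1.325 SD |
|---|---|---|
| 10 v 10 | 1.32 | 80% |
| 9 v 9 | 1.41 | 75% |
| 7 v 7 | 1.63 | 63% |
| 15 v 9 | 1.24 | 85% |
| 15 v 7 | 1.35 | 79% |
| 15 v 5 | 1.53 | 68% |

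The 15 v 5 contrast can arise with one group at its cap: 15 + 10 + 10 + 10 + 5 = 50.

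**Step 5. How often unmanaged filling would reach the floor (illustration).** Assume a hard stop at 50, equal 20% shares, arrival in random order and no dropout. Only 10/10/10/10/10 meets the floor, and the cap never binds on the way there, so the chance is 50!/[(10!)^5 × 5^50] = 0.0005. A simulation of 20,000 runs gave 0.0006, with a median smallest group of 7. The protocol gives no phenotype shares. Under assumed uneven shares (30/10/25/10/25%, and two more uneven sets), no run met the floor and the median smallest group was 2 to 4.

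**The case against.** **The three figures do not contradict one another outright.** A reader might infer that they cannot all hold. They can, at 10 in every group. This objection stands. The accurate statement is that this is the only solution, and that under it the closing rule never operates.

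**50 may not be a ceiling.** The only closing rule applies to a category. If 50 is the planned minimum (5 × 10) and 15 the limit per group, open groups keep recruiting and none loses places. The text permits that reading, so a shortfall depends on treating 50 as a hard limit. But then the total is misstated, because up to 75 women could be enrolled.

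**Filling order and rarity are not in the text.** A reader might infer first-come filling, in which common phenotypes crowd out rare ones. The protocol gives neither a filling order nor phenotype frequencies, and sites could balance recruitment from their lists. This objection stands: the rule allows the outcome but does not show that it will happen.

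**Losses are partly handled.** Re-enrollment after a failed bowel prep is possible, and acute illness leads to rescheduling. That reduces the gap between enrolled and completed but does not remove it, since re-enrollment is discretionary and the other reasons for stopping remain.

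**Not every contrast suffers.** A group at 15 against one at 9 does slightly better than 10 v 10. The loss falls on contrasts between small groups and on very uneven pairs. The protocol also claims no power for any group size.

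**Conclusion.** The point holds as a defect of specification. The total, the range and the closing number in Section C.1 agree only at exactly 10 per group, and the stated range implies 50 to 75 women rather than 50. That conclusion is pure arithmetic and needs no assumption.

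Groups below 10 are a permitted consequence, conditional on 50 being a hard limit and on recruitment not being balanced by phenotype in practice. Under the assumed test, the cost runs from none (15 v 9) through modest (9 v 9, 1.41 SD against 1.32) to material (7 v 7, 1.63 SD; 15 v 5, 1.53 SD). The documents do not support a prediction that particular phenotypes will be starved.

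Severity: should be fixed. The error affects the stated sample size and a site instruction, but the harm to the comparisons is possible rather than demonstrated.

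**What to change.** Amend Section C.1 in one of two ways.

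- **If 50 is the limit:** close each group at 10, or reserve 10 places for every group until it is formally declared unfillable and only then release its unused places.
- **If up to 15 per group is wanted:** state the total as 50 to 75 and keep closure at 15.

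In either case, use one counting unit for the total and the closing number, and name it. If the unit is completers, say that more than 50 women may need to be enrolled to replace those who do not complete.

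The text change is a sentence or two in C.1, passed on to the sites. Under the first option, easily filled groups stop at 10, or wait above 10 until places are released. Under the second, the planned total becomes a range, with up to 25 more women (75 − 50) to biopsy and process. Counting completers adds whatever replacement enrollment the losses require; the protocol gives no loss rate from which to size it.

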2. STUDY PROCEDURES

a. Pre-eligibility:

WIHS sites will be provided with lists of potentially eligible participants based on the Inclusion and Exclusion Criteria listed below. Study staff will then approach potentially eligible participants at their next regularly scheduled Core Visit. Participants who are interested will have a Pre-Eligibility Screening Interview at the end of the Core Visit. Those who appear eligible will be scheduled for a Screening Visit. (*See Appendix C: Time and Events Schedule.*)

b. Screening Visit

The Screening Visit will be scheduled as soon as possible after the WIHS Core Visit. Informed consent will be obtained at this visit. All participants will answer questions about medical history, current medications, and use of intravaginal products. Urine testing for pregnancy will be performed. Participants with a positive pregnancy test will not continue in the study. Blood will be drawn for prothrombin and partial

thromboplastin tests (PT and PTT). HIV-positive participants will have blood drawn for HIV viral load, since it is anticipated that results from the prior WIHS Core Visit will not yet be available. HIV-positive participants will also be asked to report any acute medical illnesses occurring during the study period and to avoid vaccinations during the study if this can be done without compromising their health. These measures are requested because of the potential for HIV viral load changes associated with acute medical illness and vaccination.

Participants will be instructed how to perform at-home urine testing to detect luteinizing hormone (LH). LH peaks just before ovulation, and is detectable in the urine in the early luteal phase.

Study staff will dispense Clearblue brand LH surge kits (Proctor & Gamble, Cincinnati, OH) and assist the participant in determining when to start testing. (*See Appendix D: When to Start LH Surge Testing.*) The participant will notify site staff when LH is detected in the urine, so that the Endometrial Biopsy Visit can be scheduled within 7 to 9 days, at which time the participant will be in the mid-to-late luteal phase. Participants will be encouraged to contact site staff should *any* questions or concerns arise during urine testing. Study staff may also contact participants.

Staff will also dispense Golytely laxative (polyethylene glycol) or other bowel cleansing medication, at the discretion of the site colonoscopist. You may need to get a prescription from the colonoscopist for this, your PI may write the prescription, or you may order it from your pharmacy. Participants will be given written instructions for Bowel Prep. Participants will be instructed to have a clear liquid diet the day before the Biopsy Visit and to refrain from any food or liquids at all for 8 hours before the Colonoscopy Visit. Participants will receive personal cleansing wipes for use during Bowel Prep, which will cause frequent liquid stools.

Participants who do not feel they will be able to refrain from vaginal intercourse for 72 hours before the biopsy will receive a supply of non-lubricated condoms.

c. *At Home Phase:*

Participants deemed ineligible because of screening PT/PTT or HIV viral load results will be notified by study staff. All others will be in contact with staff regarding at-home urine testing for LH surge.

Participants will receive calls from staff to assist in urine testing as needed. The Endometrial Biopsy Visit will be scheduled 7 to 9 days after LH surge. The Colonoscopy Visit will be scheduled for the same day, or within 7 days of the Endometrial Biopsy.

Participants will receive reminder calls when it is time to stop using intravaginal products, as well as when to stop using prohibited medications (those which increase risk of bleeding), when it is time to begin clear liquid diet and to begin Bowel Prep. They will also be contacted to determine if they have had any acute medical illnesses (for example, cold or flu-like illnesses, fever, diarrhea, urinary tract infections, genital herpes outbreaks, vaginitis) that would necessitate rescheduling of the Biopsy Visit.

Study staff will be available via pager to assist the participant in adherence with Bowel Prep. For participants who may find it very difficult to do the Bowel Prep at

home (for example, those marginally housed or living in places where bathroom access is limited), one option is to offer hospitalization at a local research center overnight. Sites should also consider this option for participants with very difficult peripheral venous access, for whom placement of a peripherally inserted central catheter (PICC) line is necessary. Sites with access to CTSA-funded CRCs may consider applying for overnight admission visits for participants who have difficulty traveling to study visits, or who are anticipated to have difficulty with the Bowel Prep.

d. *Biopsy Visit:*

FOR SOME SITES, IT WILL NOT BE POSSIBLE TO SCHEDULE THE COLONOSCOPY AND ENDOMETRIAL BIOPSY ON THE SAME DAY. IN THAT CASE, THE ENDOMETRIAL BIOPSY SHOULD STILL BE SCHEDULED BASED ON THE LH SURGE. THE COLONOSCOPY CAN BE SCHEDULED WITHIN 7 DAYS ON EITHER SIDE OF THE ENDOMETRIAL BIOPSY.

SITES PERFORMING GYNECOLOGICAL SPECIMEN COLLECTION WITHOUT SEDATION MAY WANT TO CONSIDER OFFERING PARTICIPANTS IBUPROFEN AND/OR PARACERVICAL BLOCK.

This visit will occur 7 to 9 days after the LH surge is detected, during the mid-to-late luteal phase of the menstrual cycle, when the depth of endometrial tissue is greatest. Participants will undergo a colonoscopy and endometrial biopsy (EMB). Immediately prior to these procedures, we will conduct a brief interview to collect health history and information on medication use and recent intravaginal product use. A urine sample will be collected to rule out pregnancy. Participants with a positive pregnancy test or recent intravaginal product use will not continue in the study.

Continuing participants will be assessed by the site colonoscopist who will determine the appropriate intravenous (IV) sedation to administer. Participants will have an IV line placed by Endoscopy Nursing staff. Before sedation is administered, blood for serum progesterone will be drawn through the IV line. Serum progesterone levels will be run locally to confirm menstrual cycle phase in case the histologic dating of the endometrium is equivocal. If colonoscopy and endometrial biopsy are being performed at separate visits, serum progesterone should be drawn at the EMB visit.

For HIV-positive participants, one 5-6 ml lavender top EDTA tube should be drawn at the same time as the serum progesterone. This will be used to compare HIV viral load in plasma to that in cervical secretions.

After venipuncture, gently invert the tube 8 to 10 times and store upright at room temperature until centrifuging. Blood should be centrifuged within 6 hours. Centrifuge at room temperature at $\leq 1300 \times g$ for 10 minutes. Aliquot at least 1.1 ml into a labeled Wheaton cryovial and refrigerate for no more than six hours before freezing at -80 for shipping.

The SF site only will also draw two 10-cc lavender top EDTA tubes for peripheral blood monocytes (PBMCs) to be shipped to the UC Davis Lab.

Sedation will be administered and blood drawn through the PICC line for those participants who required PICC placement; all peripheral and PICC lines will be

removed before the participant is discharged from the study. After sedation, the participant will be placed in a right side-lying position and a colonoscope will be passed through the large intestine and through the ileo-cecal valve. At least 8 to 10 biopsy samples each of the ileum and sigmoid colon (total 16 to 20 samples) will be obtained with cold forceps using standard techniques. In the event the colonoscopist identifies any lesions, additional biopsies of the lesion(s) will be obtained as clinically indicated, and sent for routine clinical pathology at the site.

Four to five samples will be placed in Wheaton cryovials supplied by the San Francisco site and flash frozen; four to five samples will be placed in a container of 10% formalin, and one sample will be placed in another container of 10% formalin. Sites will supply their own formalin containers. All will be shipped to San Francisco.

Endoscopy nurses are used to collecting biopsy specimens; if you give her/him the tubes, s/he will probably use a small needle to tease the tissue out of the forceps into your cryovial or container of formalin. Please collect the frozen sample first so that there is no chance of contaminating the frozen specimen with formalin. The study specimens will be used to measure inflammatory cells, cytokines and other immune markers, and collagen deposition. Routine histology will be performed on the second formalin container.

(San Francisco site only will also send fresh endometrial specimens in antibiotic medium to the [name] Lab at UC Davis.)

- If the colonoscopist determines that the Bowel Prep is inadequate to allow visualization of the colon, s/he will withdraw the endoscope; the participant will remain in the unit to recover, but no further study procedures (i.e., endometrial biopsy) will be done. Blood, if drawn for serum progesterone level or HIV viral load, will be discarded.
- After colonoscopy is completed, all gynecological specimens will be collected. The participant will be placed in the lithotomy position. A pelvic examination will be performed to rule out signs of infection; if any are present, no further procedures will be performed.

1. Endocervical wick/sponge sampling:

Endocervical mucus and secretions for analysis of cytokines will be collected with Merocel ophthalmic sponges (Medtronic Xomed, Jacksonville, FL). Using a ring forceps, two sponges will be inserted sequentially into the cervical os; each will be held in place to absorb sample for 60 to 90 seconds. The sponges are inserted gently directly into the os. The depth of insertion is based on the size of the os; in some women it is possible to insert just the tip of the sponge, while in others, the entire sponge may be inserted. The sponges should never be forced, as this may cause bleeding which will contaminate the mucus collected. They should not be twisted or turned; simply allow the sponge to rest and absorb secretions. It should be possible to see the sponge expanding as it absorbs secretions.

After removal, the sponges will be placed in separate cryovials, supplied by the San Francisco site. Place the sponge spearhead down in the vial and cut off the part of the handle that protrudes from the vial so that the sponge will fit into the

tube. Then place this cut-off handle in the vial with the sponge section and close the vial. This is necessary because the lab must weigh the whole collection device in order to ascertain the volume of fluid collected. The cryovials will be placed in liquid nitrogen and the samples will be shipped frozen.

For HIV-positive participants ONLY, endocervical mucus and secretions for HIV viral load will be collected with TearFlo ophthalmic strips. Using a ring forceps to hold three strips on the squared end of the strips, gently insert them simultaneously into the cervical os and hold in place for approximately 60 to 90 seconds to adsorb sample. Only the TearFlo strips and **not** the forceps should be placed in the cervical os. If a woman has a small or pinpoint os, gently place the tip of the TearFlo strips to the opening of the os and get as much secretion as possible. The strips may also be folded vertically to make them thinner, and thus, able to pass through the os. After removal, all three strips will be placed in one Corning cryovial with lysis buffer. Hold the round end of the three strips over and slightly inside one labeled vial. Cut the round head off the strips with sterile scissors, allowing the heads to fall into the vial. Cap the vial and gently invert five times. The cryovials will be placed in liquid nitrogen and the samples will be shipped frozen.

CAUTION: Buffer is caustic! Always wear gloves and eye protection!

2. Endocervical cytobrush sampling: (*SAN FRANCISCO SITE ONLY!*)

Two cytobrushes will be inserted into the cervix sequentially. Each will be rotated five times to collect cells. Brushes will be placed in antibiotic medium and shipped fresh to the [name] Lab at UC Davis.

3. Endometrial biopsy:

We will use the Pipelle aspirator, a flexible polypropylene sheath with an inner plunger that is attached to a syringe; the entire device is disposable. The procedure requires a total of 10 to 15 min, with 5 to 15 seconds for tissue sampling. With the participant in the lithotomy position, a bimanual exam is performed to determine uterine size and position and to determine whether marked uterocervical angulation exists. A sterile speculum is inserted and the cervix visualized. An antiseptic solution is applied to the cervix, and if it is not readily visualized, a tenaculum is used to position the cervix. The Pipelle is introduced through the cervical os, endocervical canal, internal os, lower uterine segment and into the uterine fundus. The depth of the uterus is measured (note the scale markings on the Pipelle catheter) and documented. The syringe piston is retracted, and the device is gently rotated with a gentle in-and-out motion at least four times within the upper endometrial cavity, maintaining a vacuum. The device is withdrawn when the Pipelle lumen has been filled with tissue. The sample will be dispelled with care not to contaminate the catheter so that it can be re-inserted for additional specimen collection if needed. After final withdrawal, the tip of the device is cut off and discarded. Half the specimen is discharged into a Wheaton cryovial by pushing the syringe piston. This specimen is flash frozen by placing the cryovial in liquid nitrogen. The other half is discharged into a container of

10% formalin. Again, it is important not to contaminate the frozen specimen with formalin.

After specimen collection is complete, the speculum and tenaculum will be gently removed, and swab pressure applied to any sites of bleeding.

(San Francisco site only will collect more endometrium and send fresh endometrial specimens in antibiotic medium to the [name] Lab at UC Davis.)

4. Cervical Transformation Zone Sampling:

The active cervical transformation zone is usually visible without colposcopy in younger women as a circular zone surrounding the os where the pale pink squamous epithelium (distally) meets the dark red epithelium of the columnar epithelium (proximally); this region includes the squamocolumnar junction. The active transformation zone, which includes the squamocolumnar junction at its proximal or leading edge can be more precisely delineated using Lugol's (iodine) solution. Lugol's stains mature squamous epithelium (dark brown); the active transformation zone and the columnar epithelium are non-staining. The cervix will be swabbed with Lugol's solution for disinfection and to visualize the transformation zone. Biopsies will be obtained with Tischler biopsy forceps; the longer jaw placed in the os on the columnar epithelium and the short jaw of the forceps placed on the squamous epithelium, spanning a portion of the transformation zone for each biopsy. Two adjacent cervical biopsies from the transformation zone at 12:00 and 1:00 will be obtained. The average size of a typical biopsy is approximately 2 to 3 mm³. One biopsy will be placed into a cryovial, snap frozen in liquid nitrogen, and shipped for storage in a -80 degree freezer until RNA extraction can be performed. The other biopsy will be placed in 10% formalin for histology and immunohistochemistry analyses. If the cervical transformation zone is not visible due to recession into the cervical canal (i.e., the entire ectocervix stains with Lugol's solution), biopsies will be performed at the cervical os with the long jaw of the forceps placed as deeply as possible into the endocervical canal and the short blade on the ectocervix. Silver nitrate will be applied for hemostasis.

(San Francisco site only will do an additional biopsy and send fresh cervical specimens in antibiotic medium to the [name] Lab at UC Davis.)

The participant will be sent to the recovery area, where she will be monitored for approximately 2 to 3 hours, until sedation wears off. Because of safety concerns after sedation, the participant will be advised not to drive or operate heavy machinery for 24 hours after the procedures. It is conventional for Endoscopy staff to refuse to discharge a patient who has received sedation without a responsible adult to accompany her home. The SC will arrange transportation via a medical cab service for participants who do not have a responsible adult to accompany them. Regardless of participant's transportation home, SC will be present at discharge. Furthermore, some Endoscopy staff may also require that the provider who performed the EMB clear the participant for discharge (i.e., confirm that there are no complications from the EMB), in addition to the clearance given by the colonoscopist.

The participant will be given post-procedure instructions. The SC will also contact the participant that evening, the next day, and again one and two weeks later to be sure she is not experiencing any adverse events.

3. INCLUSION CRITERIA:

1. WIHS participants between 18 and 44 years of age.
2. Regular menstrual cycles (21 to 35 days).
3. HIV-negative women *OR* women who meet the criteria for the HIV disease progression groups listed above. All positive participants must have documented HIV positivity for at least three years. (*See Appendix B for detailed definitions of the eligibility groups.*)
4. Participant must be willing and able to perform urine testing at home and to report for an Endometrial Biopsy Visit 7 to 9 days after testing confirms that LH surge has occurred, with Colonoscopy Visit occurring the same day or within seven days.
5. Participant must be willing and able to refrain from using vaginal products for 10 days prior to the Endometrial Biopsy Visit.
6. Participant must be willing and able to refrain from vaginal intercourse or to use nonlubricated condoms for 72 hours prior to the Endometrial Biopsy Visit.
7. Participant must be willing and able to perform Bowel Prep.

4. EXCLUSION CRITERIA:

1. History of hysterectomy.
2. Allergies to latex or iodine.
3. History of bleeding dyscrasias; current anticoagulant therapy or abnormal screening coagulation studies.
4. History of inflammatory bowel disease.
5. Currently breastfeeding, pregnant, or planning a pregnancy in the near future. Has breastfed in the last six months.
6. Current or recent abnormal vaginal discharge and/or abnormal vaginal bleeding.
7. Current genital herpes outbreak, and/or greater than four outbreaks/year. (Suppressive therapy for genital herpes is **NOT** exclusionary.)
8. Any active uterine or gut infection.
9. Recent (within 14 days of Biopsy Visit) upper respiratory infection, urinary tract infection, vaginitis, systemic illness with fever or diarrhea, or vaccination.
10. Abnormal Pap smear in the last 12 months.
11. Use of intrauterine device in the last 12 months.
12. Use of hormonal contraceptives or sex hormones within the last 12 months.

13. Use of supraphysiologic levels of glucocorticoid therapy or other potential immunomodulatory therapy within the past 30 days. (Use of inhaled steroids for asthma is **NOT** exclusionary.)
14. Other conditions that, in the opinion of the investigator, would compromise the participant's ability to comply with the study protocol, such as a major psychiatric disorder, or inebriation or cognitive impairment sufficient to interfere with participant's ability to give informed consent.

D. COMPENSATION

Participants will be reimbursed for the Screening Visit and for the Biopsy Visit(s) at the discretion of each site. For example, SF is reimbursing \$25 for screening and \$125 for the Biopsy Visit. Participants whose Bowel Prep is deemed inadequate to perform colonoscopy will be reimbursed \$20. The participant will be offered re-enrollment with her next menstrual cycle at the discretion of the site's Principal Investigator and the Study Coordinator.

E. SPECIMEN DISPOSITION

1. LABELING SPECIMENS:

San Francisco will supply Merocel sponges, Wheaton cryovials and cryo-labels to all the sites. They will also supply preprinted labels for the formalin containers. Sites will supply their own formalin containers. A layer of blank packing tape should be placed over the formalin container label to prevent running of the ink should containers come in contact with liquids.

San Francisco will supply cryo-labels and Corning cryovials with lysis buffer (orange cap) for collection of cervical secretions in HIV-positive participants, and cryo-labels and cryovials for collection of plasma for HIV viral load. Sites will supply their own EDTA blood collection tubes.

